4.1.2. Denominators for prevalence

For prevalence case ascertainment, the denominator includes individuals enrolled in any of the three partnering health care plans and residing on the island of Oahu during the year 2001 (Oahu residents comprise approximately 80% of the state’s population).

	Caucasian	African American	Hispanic	Asian	Pacific Islander	Native American	Total
0 thru 9	26295	3310	13733	50754	20914	319	115325
10-19	28486	3585	14877	54984	22657	346	124935
	54781	6895	28610	105738	43571	665	240260

4.1.3. Denominators for incidence

For incident case ascertainment, the denominator will include individuals enrolled in any of these three health care plans throughout the entire state of Hawaii for the years 2002, 2003 and 2004.

	Caucasian	African American	Hispanic	Asian	Pacific Islander	Native American	Total
0 thru 9	32869	4137	17166	63443	26143	399	144157
10-19	35608	4482	18596	68730	28321	433	156170
	68477	8619	35762	132173	54464	832	300327

4.2. CASE ASCERTAINMENT

4.2.1. Prevalent Cases

4.2.1.1. Case finding site-specific approaches

Variation in data sources available from each of the three health plans comprising the Hawaii study population necessitates different approaches to initial case identification. In general, the strategy for initial case identification employed with each data source is inclusive and will potentially result in the identification of cases that upon verification will be found to be false positive cases. However, the primary objective at this stage is to maximize sensitivity, at the unavoidable expense of compromising specificity.

Using plan-specific case identification criteria, insurance claims and encounter data will be requested from each of the three plans to include complete data through the end of the year 2001.

Data sources

The table below summarizes the characteristics of the data available from each of these plans relevant to the task of diabetes case identification. Case specific identifying information such as name, date of birth, and address are available from all health plans.

Data Available for SEARCH Project

	HMSA	Kaiser	Med-QUEST
Inpatient ICD-9 and CPT codes	✓	✓	✓
Outpatient ICD-9 and CPT codes	✓		✓
Pharmacy	✓	✓	✓
Lab tests ordered	✓	✓	✓
Lab test results		✓	Kaiser only
Utilization data	✓	✓	✓

Identification of duplicate cases

Given the particular data sources we will use for this project, the identification and removal of duplicate cases must be performed for both identified cases

(numerator) and for membership data (denominator). In addition, it is possible that duplicate cases may exist within individual data sources. While the specific identifiers that will be available to us for the purposes of duplicate removal prior to case validation are subject to IRB approval, we anticipate receiving name, gender, date of birth, address (with zip code) and inpatient discharge dates for all cases identified initially through data selection criteria. Since there are likely to be approximately 500 cases, computerized matching on these variables followed by visual checking is expected to be sufficient to identify duplicate cases in numerator data. Questionable cases within the same health plan source data will be referred back to the health plan for verification. Questionable cases found in two or more health plan data sources will be referred back to the health plan to check membership data for dual coverage. Previous work with similar data has revealed very few individuals receiving care in more than one plan in a given year.

The unduplication of plan membership data (denominator) will pose more challenges. It is unlikely that the health care plans will share complete listings of members with identifying information. Shared information is subject to IRB approval. In past studies we received gender, date of birth, and zip code for insurance plan members finding an overlap in membership of less than 3%. We will request these data elements again, adding as many characters of last and first names as the health plans and IRBs will permit. An automated matching process for membership data will be used due to the large volume of cases. Questionable duplicates within health plan datasets will be referred back to the plan for verification. A special process will be developed with health plan collaborators to resolve questionable duplicates identified in more than one dataset that will involve communication between the plans.

Case definition and eligibility

Cases that are between the ages of 0 and 19.999 during the selected index year (2001) will be eligible for inclusion in the study. Geographic eligibility for the Hawaii study center for prevalent cases will be limited to members of the HMSA, Kaiser Permanente and Med-QUEST health plans who reside on the island of Oahu (Honolulu County). The population of Honolulu County includes approximately 80% of the population of the entire state. All data sources to be used for initial case identification include zip codes in their membership files and Oahu residents can be readily identified on the basis of zip code.

a) Case Definition 1: HMSA Data

Designed primarily for billing purposes, this data source is typical of insurance claims datasets with considerable administrative information and little clinical information. Specific algorithms have been developed for identification of diabetic individuals using similar and sensitive data. However, the relative accuracy of these methods for identifying children with diabetes is unknown. Given the potential for misdiagnosis of hyperglycemic episodes in children we

anticipate less specificity of this method in the identification of children. Anecdotal evidence suggests a reluctance among Hawaii practitioners to utilize oral hypoglycemic agents in children however, which may result in fewer false positive cases based on this criteria in Hawaii than in other sites.

The specific criteria for initial case identification from this source include any one of the following:

- At least one prescription for insulin or oral anti-diabetic agent included in HEDIS list for the identification of persons with diabetes during the index year.
- A principal or secondary inpatient discharge ICD-9-CM diagnosis of diabetes (250.xx) during the index year. Diagnosis code 648.0x for gestational diabetes will be excluded.
- In outpatient claims, one visit with a diagnosis of diabetes (250.xx) during index year. Diagnosis code 648.0x for gestational diabetes will be excluded
- From laboratory claims or utilization files, at least two glycohemoglobin or fructosamine tests done on separate dates during the index year (CPT-4 codes 83036 or 82985).

b) Case Definition 2: Kaiser Permanente Hawaii Data

Kaiser Permanente Hawaii maintains a registry of patients with diabetes, similar diabetes registries are in use in other Kaiser regions. Eligible patients listed in this registry during the study index year will be identified as initial cases. Inclusion in this registry is based on the identification of individuals with diabetes in other databases maintained by the health plan, including pharmacy records, lab results and inpatient discharge diagnosis records. The Diabetes Registry is updated quarterly and checked against a current membership file. Cases are included in the registry once they have met any one of the criteria listed below, and remain on the registry as long as they are Kaiser Permanente members.

- An inpatient discharge ICD-9-CM diagnosis of diabetes (250.xx) during the index year. Diagnosis code 648.0x for gestational diabetes will be excluded.
- A glycohemoglobin test result ≥ 7 .
- The dispensing of an antidiabetic drug (GPI code 27xxxx).

c) Case Definition 3: Med-QUEST Data

The Med-QUEST Division of the Hawaii State Department of Human Services is not a direct provider of patient care but provides for services through contracts with six health care plans, including HMSA and Kaiser Permanente Hawaii. The Med-QUEST Division requires that all contracted plans submit a standard dataset reporting all services provided to patients insured by Med-QUEST. For purposes of identifying patients with diabetes, the MED-QUEST dataset includes all of the same data elements included in the criteria listed above for HMSA, with no

additional criteria that would be useful for case identification. For Med-QUEST patients electing to receive care by Kaiser Permanente, additional data will be available since these patients having diabetes would also be listed in the Kaiser Permanente Diabetes Registry. Therefore, the criteria for case identification for all Med-QUEST patients would include any one of the following:

At least one prescription for insulin or oral anti-diabetic agent included in HEDIS list for the identification of persons with diabetes during the index year.

- A principal or secondary inpatient discharge ICD-9-CM diagnosis of diabetes (250.xx) during the index year. Diagnosis code 648.0x for gestational diabetes will be excluded.
- In outpatient claims, at least two visits on separate dates with a diagnosis of diabetes (250.xx) during the index year. Diagnosis code 648.0x for gestational diabetes will be excluded.
- From laboratory claims or utilization files, at least two glycohemoglobin or fructosamine tests done on separate dates during the index year (CPT-4 codes 83036 or 82985).
- Inclusion in the Kaiser Permanente Diabetes Registry during the index year.

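### Hawaii's prevalent case search asks for two coded outpatient visits in Med-QUEST data but one in HMSA data, with the same data elements and no reason given

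*Protocol*

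**What the plan says.** The rules are in the Hawaii site-specific methods, section 4.2.1.1.

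- **Aim of the search.** The section says "the primary objective at this stage is to maximize sensitivity", and it accepts a loss of specificity in return.
- **Reason for plan-specific rules.** "Variation in data sources available from each of the three health plans comprising the Hawaii study population necessitates different approaches to initial case identification".
- **HMSA (Case Definition 1).** "The specific criteria for initial case identification from this source include any one of the following": a prescription for insulin or an oral agent, an inpatient diabetes code, two glycohemoglobin or fructosamine tests on separate dates, or the outpatient criterion: "In outpatient claims, one visit with a diagnosis of diabetes (250.xx) during index year".
- **Med-QUEST (Case Definition 3).** The text first says that "the MED-QUEST dataset includes all of the same data elements included in the criteria listed above for HMSA". It then says that "the criteria for case identification for all Med-QUEST patients would include any one of the following". The prescription, inpatient and laboratory criteria match HMSA's. The outpatient criterion is "In outpatient claims, at least two visits on separate dates with a diagnosis of diabetes (250.xx) during the index year". One route is added: "Inclusion in the Kaiser Permanente Diabetes Registry during the index year". It serves Med-QUEST patients who receive their care at Kaiser.

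The site's table of available data also marks outpatient diagnosis codes as present for both HMSA and Med-QUEST.

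**The concern.** The only reason offered for different rules is that the plans hold different data. That reason fails between HMSA and Med-QUEST, because the protocol says their data elements are the same. The Kaiser registry route is explained; the second outpatient visit is not. A stricter threshold in one plan also works against the stated aim of the search. Specificity is dealt with later, by letters to physicians and to patients or parents (Hawaii 4.3.1).

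The children affected have a diabetes code at one outpatient visit, no diabetes drug, no admission and little laboratory monitoring. The HMSA paragraph reports anecdotal reluctance among Hawaii practitioners to use oral agents in children, so an outpatient code may be the main way such a child enters the list. Prevalence by type is part of primary aim (a), and the site expects a sizeable type 2 group.

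There is a side effect. Hawaii 4.3.1 plans to assess the predictive value of each case-finding indicator alone. With unequal thresholds, the outpatient indicator means different things in the two plans, and a single visit alone cannot be assessed in Med-QUEST.

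**Working it through.** The protocol states no yield or sensitivity for these criteria, so there is no figure of its own to reproduce on that point.

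**Step 1. Compare the lists.** Both are satisfied by any one criterion.

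| Evidence in the index year | HMSA | Med-QUEST |
|---|---|---|
| Insulin or oral-agent prescription | at least 1 | at least 1 |
| Inpatient 250.xx code | at least 1 | at least 1 |
| Outpatient 250.xx visits | at least 1 | at least 2, separate dates |
| Glycohemoglobin or fructosamine tests | at least 2 | at least 2 |
| Kaiser registry entry | not used | sufficient |

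**Step 2. Enumerate the patterns.** Take prescription (0/1), inpatient code (0/1), outpatient visits (0/1/2+), tests (0/1/2+) and registry (0/1): 2 × 2 × 3 × 3 × 2 = 72 patterns.

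- Listed by HMSA's rule only: two patterns. Both have one outpatient visit, no prescription, no inpatient code and no registry entry, with 0 tests in one and 1 test in the other.
- Listed by Med-QUEST's rule only: two patterns, both through the Kaiser registry.

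Without the registry route, Med-QUEST's rule is a strict subset of HMSA's. For the same use of care, its sensitivity can only be equal or lower. With one visit in both lists, no pattern is found by HMSA's rule and missed by Med-QUEST's.

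**Step 3. Scale.** The Hawaii total reproduces from Tables V-1 and V-2 (rate × denominator, truncated by cell):

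- type 1: 91 + 249 = 340
- type 2: 16 + 179 = 195
- total: 340 + 195 = 535

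Hawaii 4.1.1 gives all-age, statewide memberships of about 640,000 (HMSA), 210,000 (Kaiser) and 130,000 (Med-QUEST). The Med-QUEST share is 130/(640 + 210 + 130) = 13.3%, or 0.133 × 535 ≈ 71 cases. No share is given for Oahu residents under 20, so I let it run from 13.3% to 35% (assumption). I let the fraction of those cases resting on a single outpatient visit run from 2% to 20% (assumption).

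Cases missed = 535 × share × fraction:

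- low: 535 × 0.133 × 0.02 = 1.4 (0.3% of 535)
- high: 535 × 0.35 × 0.20 = 37 (7.0% of 535)

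**Step 4. Which end is more plausible?** Assume that every type 1 child fills an insulin prescription and that Med-QUEST has the site's type mix. Only type 2 cases, 195/535 = 36%, can then be affected. A fraction of 20% would need 20/36.4 = 55% of them to have exactly one coded visit, no drug, no admission and fewer than two tests. A fraction of 2% needs 2/36.4 = 5.5%. Step 3 also counts Med-QUEST children in Kaiser, who have the registry route, and allows nothing for recovery by other sources. All three considerations point to the low end.

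**The case against.** Several points on the other side are sound.

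- **A single code can be a false alarm.** The Puget Sound section (4.3.2) names the rule-out diagnosis as a problem with single codes and requires a pharmacy fill as well. A two-visit rule is a recognisable response. But Hawaii does not invoke it for Med-QUEST, and it would apply equally to HMSA. Hawaii's own worry about specificity in children appears in the HMSA paragraph, where the one-visit rule is adopted. This could justify a common rule, but not two different ones.
- **Kaiser has no outpatient-code route at all.** This stands. On outpatient codes Med-QUEST lies between HMSA and Kaiser, while Kaiser has laboratory results and a persistent registry. A reader might infer that publicly insured children, and so poorer or minority children, are less likely to be found than privately insured ones. The protocol does not support that: the net ordering of the three plans is unknown, and nothing links the rule to income or race.
- **Other routes exist.** A reader might infer that these children can never be counted. That is too strong. Table 4-1 marks an endocrinology case list and other sources for Hawaii. Hawaii 4.3.2.1 adds list checks by physicians, the statewide discharge file, and contact with diabetes educators and school nurses. HMSA is also a Med-QUEST contractor, so some children might appear in its files; the protocol does not say. Recovery is nevertheless partial. The physician check goes only to those treating three or more validated cases, the discharge file cannot show a child with no admission, and the yield of the rest is not stated.
- **The reach is small.** This concerns one site, prevalence only, and one narrow pattern of evidence. Poisson error on 535 cases is already ±1.96/√535 = ±8.5%. That limits the importance of the point. It does not excuse an avoidable downward bias.

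**Conclusion.** The inconsistency is exact and its direction is settled. For Med-QUEST children not cared for at Kaiser, the claims criteria are a strict subset of HMSA's, differing only for the child with a single coded outpatient visit. Hawaii 4.1.2 keeps these children in the prevalence denominator, so any that are not recovered elsewhere bias prevalence downward.

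The size is not known. The range of about 1 to 37 of 535 cases rests on an assumed Med-QUEST share (13% to 35%) and an assumed single-visit fraction (2% to 20%). The low end is more likely. Incident case finding in Hawaii, which relies on network reporting, is not affected. The point is worth correcting because the remedy is simple, not because the expected loss is large.

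**What to change.** In Hawaii 4.2.1.1, Case Definition 3, replace the two-visit outpatient criterion with the one-visit criterion used for HMSA, and let the existing physician and patient/parent validation remove false positives.

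Section 10.3 dates prevalence ascertainment to December 2001, while the Hawaii text is still in the future tense, so the state of the Med-QUEST extract is unclear. If it has already been drawn, re-run it with the one-visit rule, or identify the one-visit-only children and report Hawaii prevalence with and without them as a sensitivity analysis.

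The cost is one changed criterion and some additional Med-QUEST candidates to validate. If the extract is already complete, add a repeat data request and a further round of letters. Equal outpatient rules cannot be extended to Kaiser, which has no outpatient diagnosis codes; the text should say so.

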[name] of the Kuakini Medical Center is the only pediatric endocrinologist in Hawaii and a consultant on the SEARCH Project. [name] will play an important role in the network core contributing newly diagnosed cases from his practice, pending IRB approval of appropriate consent procedures.

The Kapiolani Medical Center for Women and Children, a specialty hospital and clinic in Honolulu, provides inpatient and outpatient services to women and children. The PHRI has a history of partnership in collaborative studies with physicians and one or more representatives from this medical center, including Co-Investigator [name]. They will be included in the network core group to facilitate physician reporting at Kapiolani.

We will utilize administrative data from HMSA and the Med-QUEST health plans to identify additional physicians who are likely to initially diagnose children and youth with diabetes. SEARCH Co-Investigators Drs. [name] of the Med-QUEST Program, and [name] of HMSA, and consultant [name] of HMSA, we assist in identifying physicians treating cases of children with diabetes state-wide, for inclusion in the broader reporting network.

An early task of the core network will be to identify ways to encourage the state-wide physician participation in reporting incident cases. As part of the ascertainment of typology, the provision of antibody testing is one incentive that will encourage participation. Other possible incentives and methods will be considered to encourage broad project participation. This group will also assist in the development of a standardized form for physicians to report cases and reporting processes (i.e., mail, phone, electronic reporting) to facilitate the process.

Case definition and eligibility

Cases that are between the ages of 0 and 19.999 during the selected index year (2002) with a clinical diagnosis between 1/1/2002 – 12/31/04 are eligible for study inclusion. Geographic eligibility for the Hawaii study center for incident cases will include members of the HMSA, Kaiser Permanente and Med-QUEST health plans who reside in the state of Hawaii.

4.3. CASE VALIDATION

4.3.1. Site-specific methods

Most, if not all, incident cases will be reported by physicians and therefore meet the study physician diagnosis validation criteria. However, medical record reviews will be performed for incident cases (with patient/parent consent). This review provides an opportunity for case validation through confirmation of diagnosis in the medical record.

We will use a multi-step process to validate prevalent cases in conjunction with our collaborating health plans.

Physician letters - Based on lists of initially identified cases, letters will be sent to individual physicians who treated identified patients during the index year. (Primary care physicians or the physician who the patient has seen most often will be used whenever possible). Physicians will be asked to verify the diagnosis of diabetes for each patient listed, and indicate the diabetes type.

Patient/parent letters - At the same time physicians are contacted, letters will be sent to identified patients or parents explaining the study. This letter will include a reply card asking for verification of physician diagnosis of diabetes and a telephone contact number for an interview. Patients/parents will be told that they will be called requesting an interview unless they specifically refuse (pending IRB approval).

This strategy of case validation will maximize the opportunity for case validation (through physician confirmation, chart review and/or self-report of physician diagnosis). In addition, this approach will facilitate the estimation of positive predictive value of each method of case identification and the development of efficient and accurate algorithms. Each initial indicator of diagnosis (inpatient and outpatient diagnosis codes, pharmaceutical data, laboratory data, self-report and primary physician confirmation) will be assessed individually and in combination for positive predictive value.

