4.2.1.3. Case Validation

It is important that cases of diabetes be true cases of diabetes. For prevalent cases, the information that is necessary to establish that the case meets the ADA criteria for diabetes will not be accessible, due to lack of chart review.

Prevalent cases of diabetes are validated if the case has either:

- a. a physician diagnosis of diabetes; or
- b. parent or youth self-reports a physician diagnosis of diabetes at the time of an interview or survey.

A “physician diagnosis” of diabetes is made if any of the following conditions are met:

- a. review of any medical record reveals a physician diagnosis of diabetes;
- b. the diagnosis of diabetes is directly verified, or the diabetes case is “referred” to the study, by a clinician;

- c. diabetes is listed as the underlying or contributing cause of death on a death certificate;
- d. the case is included in a clinical database that has a requirement for verification of diagnosis by a clinician.

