4.2.4. Gestational Diabetes

The study will not attempt to ascertain gestational diabetes, defined as diabetes mellitus with onset or first recognition during pregnancy. When case finding approaches identify gestational diabetes, these will be excluded. However, in some situation, women with gestational diabetes may wrongly be assigned diagnostic codes for diabetes. During the validation process (chart review and/or survey), these cases will be identified and then excluded from SEARCH.

If a woman's diabetes is first recognized during pregnancy and persists after the pregnancy ends, the case will be registered. The onset date will be defined as the date of first clinical diagnosis of diabetes in the non-pregnant state (usually at the first post-partum visit).

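### Hawaii's planned positive predictive value for self-report and for physician confirmation is 100% by construction, because either one alone validates a case

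*Protocol*

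**What the plan says.** Section 4.2.1.3 (Case Validation) sets the study-wide rule. "Prevalent cases of diabetes are validated if the case has either" a physician diagnosis or a self-report of one. The self-report route is worded "parent or youth self-reports a physician diagnosis of diabetes at the time of an interview or survey". A physician diagnosis can be reached in four alternative ways, one of which is that "the diagnosis of diabetes is directly verified, or the diabetes case is “referred” to the study, by a clinician". The same section also states a limit on the prevalence component: "the information that is necessary to establish that the case meets the ADA criteria for diabetes will not be accessible, due to lack of chart" (that is, records will not be examined for this purpose).

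Hawaii 4.3.1 (Site-specific methods) applies this rule by writing to the treating physicians and, at the same time, to patients or parents, who get a reply card. The stated intent is to "maximize the opportunity for case validation (through physician confirmation, chart review and/or self-report of physician diagnosis"). The section adds that the approach will support "estimation of positive predictive value of each method of case identification and the development of efficient and accurate algorithms". It then names the indicators: inpatient and outpatient codes, pharmacy data, laboratory data, "self-report and primary physician confirmation) will be assessed individually and in combination for positive predictive value". It names no separate reference standard for the PPV.

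**The concern.** PPV is the share of indicator-positive youths who turn out to be valid cases. It is informative only if the outcome can disagree with the indicator. Here two of the indicators are themselves routes to the outcome, so they cannot fail. This is incorporation bias in its complete form.

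The stated purpose is to develop accurate algorithms, and the site expects false positives. Hawaii 4.2.1.1 says that initial identification puts sensitivity ahead of specificity, and it anticipates lower specificity in children for the insurer's claims data. A results table with 100% for self-report and physician confirmation beside lower figures for codes and prescriptions could be read as evidence that the replies are accurate, when no reply could have produced any other figure. Hawaii 4.3.1 also gives no rule for a positive family reply that meets a negative physician reply. Such a case is valid under Section 4.2.1.3 and would count in favour of self-report.

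**Working it through.** The protocol states no PPV figure, so there is none to reproduce. The check is of the definition.

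**Inputs**
- Valid case: V = P or S or C, where P is physician confirmation, S is self-report of a physician diagnosis and C is a diagnosis found on chart review (Section 4.2.1.3; Hawaii 4.3.1). The remaining routes in 4.2.1.3, death certificate and clinician-verified database, only add further ways to be valid and do not change the result for S or P.
- Administrative flag: A, meaning a code, prescription or laboratory criterion (Hawaii 4.2.1.1). A is not a route to V.

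**Formula.** PPV(X) = P(V | X positive). If S is positive, V holds by definition, so P(V | S) = 1. The same is true of P, and for any other indicator X, P(V | S and X) = P(V | P and X) = 1.

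**Enumeration of the 16 patterns of A, P, S and C.** The counts show which patterns are logically possible; they are not probabilities.

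| Indicator positive | Patterns | Valid | PPV against the protocol's rule |
|---|---|---|---|
| S | 8 | 8 | fixed at 100% |
| P | 8 | 8 | fixed at 100% |
| S and P | 4 | 4 | fixed at 100% |
| A and S | 4 | 4 | fixed at 100% |
| A and P | 4 | 4 | fixed at 100% |
| A | 8 | 7 | free to vary |

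For A, the one invalid pattern is a flag with no confirmation from any source, so its PPV can be estimated from data.

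**What an independent reference would allow (illustration on assumed values, none from the protocol).** Let t be the share of flagged youths who truly have diabetes, se the sensitivity of the reply and fp its false-positive rate. Then PPV = se·t / (se·t + fp·(1 − t)). With se = 0.95:
- t = 0.6, fp = 0.10: 0.570 / (0.570 + 0.040) = 93.4%
- t = 0.9, fp = 0.02: 0.855 / (0.855 + 0.002) = 99.8%

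Against the protocol's rule, both settings give 100%. The illustration shows only that the planned figure cannot respond to the error rate. It does not estimate that rate.

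**Scale.** Table 3-1 expects 535 of 6,378 prevalent cases in Hawaii: 535 / 6,378 = 8.4%.

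**The case against.** The strongest reply is that Hawaii 4.3.1 never says in so many words that PPV is taken against validation by any route. Self-report could be judged against the physician's reply or the chart, which would be informative, and the choice of reference might be left to an analysis plan. This does not carry. The section presents the validation strategy itself, with its three alternative routes, as what makes PPV estimation possible, and Section 4.2.1.3 is the only standard given. Chart review appears as one more way to be valid, not as a referee. The plan states the indicators, the measure and the purpose, and on its own terms the result is circular.

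Other parts of the objection stand:
- Self-report and physician confirmation are not case-finding criteria in Hawaii. Those are prescriptions, codes, laboratory tests and registry listing (Hawaii 4.2.1.1). The replies are sought only after a youth has been flagged, so they do not compete with codes for finding cases.
- Table 5-1 already records the method of validation at case registration, self-report included.
- Gestational cases are an exception at the margin: "During the validation process (chart review and/or survey), these cases will be identified and then excluded from SEARCH". PPV for an eligible, registered case can therefore fall somewhat below 100%; PPV for a validated case cannot.

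A reader might infer more than this. One inference is that all of Hawaii's PPV work is void, but codes, pharmacy and laboratory data are not routes to validation. Another is that the prevalence estimate is distorted, but no PPV from this section is stated to enter a rate, an adjustment or an eligibility decision. A third is that every combination requiring self-report hides the same error as self-report alone. That does not follow: self-report together with an insulin prescription would in general have a different true PPV. Nor do the documents give any error rate for self-report from which to size the hidden error.

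**Conclusion.** The point holds as a limited one. For self-report, physician confirmation and any combination that requires one of them, the planned PPV for a validated case is 100% by construction and carries no information about accuracy. This rests on one premise: that the reference is the either/or rule of Section 4.2.1.3, the only one the protocol supplies. It needs no assumption about error rates.

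The consequence is confined to the algorithm evaluation at one site. PPV of diagnosis codes, pharmacy and laboratory data, alone or combined with each other, can still be estimated, although it remains PPV against the either/or rule. Prevalence is not affected by the circular figures. This is a low-priority correction.

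**What to change.** In Hawaii 4.3.1:
- Restrict the PPV analysis to the claims, pharmacy and laboratory indicators, alone and combined with each other, and name the validation rule of Section 4.2.1.3 as the reference.
- Report self-report against physician confirmation or chart review as a cross-tabulation, in the cases where both are available.
- Use the validation method recorded at registration (Table 5-1) to show how many cases rest on self-report alone, and add a count of those with a conflicting physician reply.

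The cost is a sentence or two of wording and one cross-tabulation. The physician and family replies are already to be collected; the only addition is to keep negative physician replies in a form that can be tabulated.
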